**AIM 2: Translate and equate HRCA swallow signal signatures to validated measures of swallowing impairment. Hypothesis: HRCA cutoffs will be significantly associated with validated VF-derived OPD impairment cutoffs.** Accomplishment of this aim positions us to establish independent HRCA cutoffs for levels of OPD severity that differentiate clinically significant OPD and aspiration from benign swallowing impairments.

**AIM 3: Prospectively assess the effectiveness of our HRCA system in predicting clinically significant OPD and aspiration in a randomized, controlled trial. Hypothesis: HRCA, will detect significantly more OPD and significantly more non-OPD, compared to SIS alone.** For this major step, we will deploy combinations of HRCA and SIS with consenting patients, and compare all screening predictions (SIS, HRCA, SIS + HRCA) to VF data from all participants.

[figure not shown]
The outcome of this research will be a clinically accurate, inexpensive, and noninvasive HRCA screening tool that will fundamentally advance efforts to reduce morbidity and mortality caused by OPD. The positive translational impact of this work is the melding of engineering (HRCA) with the clinical (SIS) screening processes. This major technological leap will elevate the current standard of patient care by ensuring that patients with OPD are correctly identified before adverse events can occur, patients without OPD are not unnecessarily deprived of food more accurately than current methods, as well as lowering health care expenditures and lengths of stay and improving quality of lives.

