### AIM 3: Prospectively assess the accuracy of our HRCA system in predicting clinically significant dysphagia and aspiration in a randomized, controlled trial.

**A3.a. Introduction:** For Aspirometer-based swallowing screening to be useful in clinical settings, it needs to outperform SIS in identifying patients at risk of silent aspiration and clinically significant dysphagia before they are placed at risk of aspiration pneumonia, or its further development is not warranted. The objective of this aim is to establish the superiority of dysphagia screening with the Aspirometer to the existing non-instrumental SIS protocols. To attain the objective of this aim, we will test the working hypothesis that the Aspirometer combined with, and independent of, SIS will identify VF-confirmed clinically significant OPD more accurately than SIS alone. We will use an approach that screens consenting patients with ordinary SIS and HRCA, and compare four levels of screening predictions (SIS human judgment criterion only, HRCA criterion only, SIS and HRCA criteria, SIS or HRCA criteria) for identifying dysphagia as measured from gold standard VF testing of all participants performed within 24 hours of screening. The rationale for this aim is that a clinically useful and accurate HRCA-based instrumental screening method not only needs to be rigorously tested against current practices to establish its validity and accuracy, but also needs to be examined for possible incorporation into current clinical practices. The acquisition of such knowledge is critical to the improved mitigation of unnecessary and adverse health sequelae associated with OPD. Based on our preliminary data, we expect that HRCA-based screening will be able to identify (sensitivity=) 90% or more of patients with OPD needing intervention or follow-up with gold standard VF testing and (specificity=) 90% of those not needing VF testing using one of the 3 strategies incorporating HRCA. This would validate the development of HRCA-based swallow screening tools that pre-emptively identify patients with a high pneumonia risk due to OPD, expedite intervention or gold standard swallowing diagnostic tests when necessary, and to reject the need for VF testing when unnecessary.

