**Table 3 – Sensitivity and specificity of screening protocols for aspiration.**  
SENS = Sensitivity; SPEC = Specificity; FPR = False Positive Rate; FNR = False Negative Rate.

Test	SENS	SPEC	FPR	FNR
Volume-Viscosity Screening Test	100%	29%	72%	0%
Daniels Swallow Screen	92%	66%	33%	8%
Gugging Swallow Screen	100%	50%	50%	0%
Yale Swallow Protocol	100%	44-64%	36-56%	0%

classified) and specificity (the percentage of patients without an underlying problem, who are correctly classified). When compared to blinded ratings of nonconcurrent instrumental exams, swallow screenings err on the side of over-identifying aspiration risk, i.e., good sensitivity but poor specificity (see Table 3). While it may be argued that this bias in favor of sensitivity constitutes a conservative “safety net” for finding swallowing difficulties, it also results in unnecessary interventions for patients without significant OPD (Figure 3) including withholding oral dietary intake and diet texture restrictions, placement of feeding tubes, and unnecessary referrals for costly assessments, all of which affect quality of life and place financial and other burdens. A screening protocol should be performed in ordinary settings by typical screening staff, and detect OPD accurately while incurring minimum risk for the patient. Our approach to this aim will produce results that can demonstrate superior identification of both people with and without OPD compared to prior OPD screening research which exhibits zero identification of silent aspiration and only about 60% identification of those without OPD.

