**A3.e. Data interpretation:** We will fit a series of logistic regression models with presence/absence of clinically significant OPD/aspiration as the dichotomous dependent variable, and HRCA signatures and SIS, both individually and in combination, as the independent variables. We will use areas under ROC curves (c-statistics) as measures of predictive accuracy, and compare them using DeLong's method [133]. We anticipate that the c-statistics for the 3 models involving HRCA will be significantly greater than that using SIS alone.

**A3.f. Expected outcomes:** The benchmark for success of Aim 3 will be a successful completion of proposed testing of the HRCA-based screening in a clinical setting yielding accurate identifications of patients at risk of silent aspiration. Specifically, we will: (1) test the HRCA-based screening in clinical settings and denote its accuracy; (2) understand if confounding clinical factors can affect the deployment of the HRCA-based screening (not expected from our preliminary work). Successful completion of this aim will demonstrate that the Aspirometer (HRCA and advanced data analytics) can conveniently, noninvasively, and inexpensively produce robust predictions of OPD presence and absence that are measurably superior to SIS, and produce some diagnostic results currently possible only with VF testing.

**A3.g. Challenges and contingency plans:** The preliminary results (see A3.c.) strongly support our hypothesis (see A3.a.). In the highly unlikely event that our judges' PA or MBSImP score ratings drift unacceptably, we will increase surveillance on inter- and intra-rater reliability and pull judges from analysis and retrain them to criterion, retest their reliability before placing them back online.

**A3.h. Sample size justification:** We plan to recruit 50 patients, with an anticipated effective sample size of 46 after refusals. Assuming that approximately 50% of recruits will have clinically significant dysphagia/aspiration, a correlation of approximately 0.3 between SIS and HRCA, and an area under ROC curve of  $c=0.600$  for SIS alone, with the proposed sample size, we will have 80% power to detect an increase in area under ROC curve as small as 0.240 at  $\alpha=0.05$  with one of the 3 strategies that involve HRCA [134, 135].

**Project coordination and management:** [name] will direct the study and will lead the analysis and algorithm

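### The Aim 3 hypothesis claims gains over SIS in both sensitivity and specificity, but the only planned test compares c-statistics, which can rise while one of the two falls

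*Combined protocol and SAP*

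**What the plan says.** The Specific Aims state the Aim 3 hypothesis in two directions: "HRCA, will detect significantly more OPD and significantly more non-OPD, compared to SIS alone". A3.b repeats both halves ("superior identification of both people with and without OPD compared to prior OPD screening research"), and so does A3.f ("robust predictions of OPD presence and absence that are measurably superior to SIS").

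A3.a words its working hypothesis more softly, as identifying OPD more accurately than SIS alone. A3.d gives improved accuracy as the main goal, and A3.g points back to A3.a for the hypothesis. A3.a also sets out to "compare four levels of screening predictions (SIS human judgment criterion only, HRCA criterion only, SIS and HRCA criteria, SIS or HRCA criteria", and expects at least 90% sensitivity and "90% of those not needing VF testing using one of the 3 strategies incorporating HRCA".

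For the analysis, A3.e fits logistic models and says "We will use areas under ROC curves (c-statistics) as measures of predictive accuracy, and compare them using" DeLong's method. It adds: "We anticipate that the c-statistics for the 3 models involving HRCA will be significantly greater than that using SIS alone". A3.h powers only the difference in area under the curve. STEP 6 of A3.d says that results will be compared, and A3.f that accuracy will be denoted. Neither names a test or an interval for sensitivity or specificity.

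STEP 3 of A3.d records the HRCA output for each swallow. Aim 3 gives no HRCA cutoff and no rule for turning swallow results into one result per patient.

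**The concern.** Detecting more OPD is a claim about sensitivity, and detecting more non-OPD is a claim about specificity. The hypothesis calls each one significant. A c-statistic averages over both, so a large gain in one can outweigh a loss in the other.

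For a screening tool the two errors have different consequences. A significant c-statistic could be reported as support for the Specific Aims hypothesis when HRCA misses more patients with OPD than SIS does, or clears fewer patients without it. A3.b describes existing screens as sensitive but not specific, so the sensitivity half may be the harder one to win.

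**Working it through.** **Inputs.** A3.h gives 46 evaluable patients, about 50% with OPD (so 23 per VF status), SIS c-statistic 0.600, SIS-HRCA correlation about 0.3, detectable gain 0.240, alpha 0.05 and 80% power. Table 4 gives HRCA per participant as 100% sensitivity and 54% specificity.

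**1. The plan's own power.** Use the Hanley-McNeil variance with n = 23 per status:
V(A) = [A(1-A) + 22(A/(2-A) - A²) + 22(2A²/(1+A) - A²)] / 23².
- V(0.600) = 0.00705 and V(0.840) = 0.00358.
- Variance of the difference = 0.00705 + 0.00358 - 2(0.3)√(0.00705 × 0.00358) = 0.00761, so SE = 0.0872.
- z = 0.240/0.0872 = 2.75, and two-sided power is Φ(2.75 - 1.96) = 78.5%.

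This agrees with the stated 80%. The power statement is not the problem.

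**2. What a gain of 0.240 can contain.** For a pass/fail test, AUC = (sensitivity + specificity)/2. A c-statistic of 0.600 fixes only the sum, at 1.20. Take as an assumption SIS sensitivity 0.92, the lowest in Table 3. Specificity is then 1.20 - 0.92 = 0.28.
- SIS: (0.92 + 0.28)/2 = 0.600.
- HRCA at 0.80/0.88: (0.80 + 0.88)/2 = 0.840.
- AUC +0.240, specificity +0.60, sensitivity -0.12.

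Hand check of the DeLong result with independent tests within status:
- Sensitivity variance = 0.92(0.08) + 0.80(0.20) = 0.2336; specificity variance = 0.28(0.72) + 0.88(0.12) = 0.3072.
- SE = √[(0.2336 + 0.3072)/(4 × 22)] = 0.0784.
- z = 0.240/0.0784 = 3.06, so superiority is expected in about Φ(1.10) = 86% of trials.

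Simulation gives about 85% at correlation 0 and 94% at correlation 0.3 between the binary results. In the same trials an exact McNemar test almost never finds HRCA more sensitive (0.01% or less).

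**3. The other half.** A3.b puts correct identification of people without OPD at about 60% in prior screening research. With c = 0.600 that implies sensitivity 1.20 - 0.60 = 0.60 (again an assumption for the institutional SIS). Against Table 4's HRCA (1.00/0.54):
- AUC = 0.77 against 0.60, a gain of 0.17; specificity -0.06.
- DeLong declares superiority in about 48% of trials (correlation 0) to 57% (0.3). Both paired tests succeed in under 0.5%.

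Table 4 also prints a false positive rate of 48%, which implies specificity 52%. Then the gain is 0.16, specificity falls 8 points, and DeLong succeeds in about 43-52%.

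**4. A case without conflict.** HRCA 0.90/0.90 against SIS 0.60/0.60 gains 0.30 on AUC and 30 points on each half.

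**5. The combined rules.** A patient positive under AND must be SIS-positive, so AND cannot exceed SIS sensitivity. A patient negative under OR must be SIS-negative, so OR cannot exceed SIS specificity. Of the three HRCA strategies, only HRCA alone can meet both halves.

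**The case against.** **The operative hypothesis is accuracy.** A3.a, A3.d, A3.g and A3.h are consistent with one another, and DeLong on c-statistics is a reasonable test of that hypothesis. This stands. The mismatch is with the Specific Aims hypothesis and its echoes in A3.b and A3.f, and rewording those would resolve it.

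**HRCA may enter as a continuous score.** Then the sensitivity loss depends on the cutoff. For an equal-variance binormal score with AUC 0.84 (an assumption), the separation is √2 × Φ⁻¹(0.84) = 1.41. At specificity 0.28 its sensitivity would be Φ(1.41 + 0.58) = 0.98, above 0.92. So the losses shown are possible, not inevitable. But A3.a speaks of an HRCA criterion, a screen acts at a cutoff, and the c-statistic does not show which result that cutoff gives.

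**Stronger readings the documents do not support.**
- A reader might infer that the AND and OR strategies are undefined. A3.a names them as Boolean rules, and the three HRCA models in A3.e can be the results of HRCA alone, AND and OR. What is missing is narrower: the HRCA cutoff and the swallow-to-patient rule.
- A reader might set the 90%/90% expectation against Table 3 and conclude that HRCA would be less sensitive than SIS. Table 3 ("Sensitivity and specificity of screening protocols for aspiration") lists published screens, not the institutional SIS. Their AUCs, 0.645 to 0.82, all exceed the 0.600 in A3.h, and A3.a expects 90%/90% from one of three strategies, not from HRCA alone.
- A reader might infer that several HRCA signatures will be refitted on 46 patients, inflating the c-statistic. A3.a, STEP 3 of A3.d and the single correlation in A3.h point to one pre-trained output, and no number of regressors is given.

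**Conclusion.** The point holds in a limited form. Nothing in the Aim 3 analysis tests either half of the Specific Aims hypothesis, and a significant DeLong result would not establish both. The planned test does match the softer hypothesis in A3.a, and its stated power is sound.

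The illustrated sizes (superiority declared in about 85-94% of trials with sensitivity 12 points lower, and in about 48-57% with specificity 6 points lower) rest on pass/fail results, 23 patients per status, within-status correlation 0 to 0.3 and assumed SIS splits with c = 0.600. They show what can happen and are not forecasts: at 0.60/0.60 against 0.90/0.90 both halves improve. The logical point does not depend on these assumptions. This should be fixed, because it governs what a positive result may be said to show.

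**What to change.** 1. Keep DeLong as the powered analysis, and state that it supports overall accuracy only.
2. For HRCA alone, fix the cutoff and the swallow-to-patient rule from Aims 1-2 before Aim 3 data are seen. Add secondary paired exact McNemar comparisons against SIS: sensitivity in VF-positive and specificity in VF-negative patients, with confidence intervals. Claim the Specific Aims hypothesis only if both are significant; since both are required, no alpha adjustment is needed. Otherwise word that hypothesis and A3.f as overall accuracy.
3. Apply AND and OR as 2x2 rules on per-patient pass/fail results. Report paired differences in sensitivity and specificity with intervals only, without superiority tests.

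**Cost.** Plan wording and routine computation on data already to be collected. The drawback is low power, which should be stated. For an assumed 0.60 against 0.90 with 23 per status, exact McNemar power is:

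| Correlation between SIS and HRCA | Each half | Both |
|---|---|---|
| 0 | 52% | 27% |
| 0.3, latent | 58% | 34% |
| 0.3, between binary results | 66% | 44% |

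A3.h does not say which correlation it means, so the range should be shown. With HRCA at 0.90/0.90, power for both falls to about 5% if SIS is 0.80/0.40 and to about 0.1% if it is 0.92/0.28. A non-significant result would therefore not show that HRCA is no better, which is why these comparisons are secondary.

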screening (SIS) protocols for OPD are present in many settings [14, 15]. Published, validated SIS’s [21-23] are based on human observations of patients swallowing water, observing for signs of OPD using standard procedures (Figure 2). SIS performed by ordinary observers (nurses, nursing assistants) relies on whether the patient coughs or chokes during or after swallowing to predict aspiration (Figure 3). Patients who “fail” SIS all receive interventions to mitigate pneumonia risk including gold standard testing using VF, to guide these interventions, whether or not they have OPD. Patients who “pass” SIS (no coughing or choking) either do not aspirate, or they have undetected silent aspiration (which occurs in up to 40% of aspirators), and resume unsafe oral intake without intervention [16]. Popular, but weak, SIS signs of aspiration such as “wet voice quality” after swallowing, have not proven sufficiently reliable as valid predictors of aspiration [17]. A “wet voice” is absent in up to 80% of thin-liquid aspiration events,

described weaknesses, adherence to the screens' protocols varies [5, 24], reducing the validity and precision of SIS. **No currently available SIS can identify silent aspiration or OPD-related** risk of pneumonia, malnutrition, and dehydration [25, 26]. Thus, an inexpensive and accurate silent aspiration detection tool is needed and our research has produced strong lines of evidence toward that end. Our scientific premise is that the Aspirometer, an accurate, early-warning, easy to use, noninvasive tool to detect silent aspiration and OPD, can lead to pre-emptive identification of silent aspirators and significantly reduce morbidity, mortality, and health care expenditures.

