### **A3.d. Experimental approach:** The main goal of this aim is to demonstrate that the proposed HRCA tool is objective and can improve upon the accuracy of SIS alone in identifying participants who have OPD and need to undergo a VF exam or need immediate intervention (Figure 11). To achieve this goal, we will carry out the following experimental steps:

STEP 1: Enroll 50 consenting patients eligible for SIS in the experiment, and perform combined SIS screening and an HRCA screening. STEP 2: The HRCA system will be applied to all patients. The dysphagia SIS screen employed in the University of Pittsburgh Medical Center Presbyterian University Hospital will be performed, which consists of two or three 5mL water swallows and drinking 90mL of water at a self-selected pace. STEP 3: Nurses or other staff (non-SLPs or physicians) administering the screens and blinded to the HRCA output, will score the screens on the basis of the institutional SIS algorithm, denoting any signs of OPD or penetration/aspiration (e.g., wet voice, coughs) for each swallow that is observed. For the concurrent HRCA screening, we will record and denote the output of the algorithm for each observed swallow with findings from Aims 1 & 2. STEP 4: We will administer a VF exam for all patients using clinical protocols that include the same bolus conditions (5mL thin liquid, 30mL thin liquid) of swallowed material used in the SIS, within a 24-hour period to confirm the presence or absence of dysphagia/aspiration. STEP 5: The MBSImP, the PAS and the Normalized Residue Ratio Scale will be used to measure swallow impairment, airway protection and post-swallow pharyngeal residue. These measures will be made by our trained laboratory associates. STEP 6: HRCA, SIS, and VF results will be compared.

**Table 4 –** HRCA-based screening can detect aspiration, validated against concurrent VF. SENS = Sensitivity; SPEC = Specificity; FPR = False Positive Rate; FNR = False Negative Rate; PB = Per bolus; PP = Per participant.

Parameter	Statistic	PB	PP
Impaired Swallowing Safety (13/40 patients; 55/154 swallows)	SENS	90%	100%
	SPEC	77%	54%
	FPR	23%	48%
	FNR	10%	0%

**Figure 12 –** Our proposed experimental and data analysis approach for Aim 3.

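### Aim 3 compares c-statistics without fixing how HRCA and SIS are coded, so a larger HRCA area need not mean better detection than SIS at a working cutoff

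*Combined protocol and SAP*

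**What the plan says.** A3.e fits logistic models for the presence of clinically significant dysphagia or aspiration, with "HRCA signatures and SIS, both individually and in combination, as the independent variables". On accuracy it says "We will use areas under ROC curves (c-statistics) as measures of predictive accuracy", and it will "compare them using DeLong's method". It expects the three models involving HRCA to beat SIS alone. The coding of the two predictors is not given.

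Other sections bear on the coding:

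- The Significance section treats SIS as a pass/fail result: "Patients who “pass” SIS (no coughing or choking) either do not aspirate, or they have undetected silent aspiration".
- A3.d, STEP 3 has staff who "will score the screens on the basis of the institutional SIS algorithm, denoting any signs of OPD or penetration/aspiration", noted for each swallow. For HRCA, "we will record and denote the output of the algorithm for each observed swallow with findings from Aims 1 & 2". Whether that output is a class or a score is not stated.
- A3.a lists the predictions to be compared as "SIS human judgment criterion only, HRCA criterion only, SIS and HRCA criteria, SIS or HRCA criteria", and expects 90% sensitivity and 90% specificity from one of the three strategies that use HRCA.
- The Aim 3 hypothesis in the Specific Aims is that HRCA will detect significantly more dysphagia and significantly more non-dysphagia than SIS alone.
- A3.h plans for 46 evaluable patients, about half with dysphagia, a correlation of 0.3, c = 0.600 for SIS, and 80% power for an increase of 0.240.

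**The concern.** The hypothesis and the 90%/90% target describe performance at a working cutoff. The planned test compares whole areas under ROC curves. These agree only if the two tests enter in the same form.

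A pass/fail test has a single operating point, so its c-statistic is the average of its sensitivity and specificity. A graded score is credited for every possible cutoff. If its ROC curve is concave and passes through the same operating point, its area is at least as large, whatever the distribution. In A1 and A2, signatures are signal features, so the natural reading of A3.e is a graded HRCA against a pass/fail SIS. On that reading, part of any HRCA advantage reflects the number of score levels, and a significant area difference does not by itself show that more patients are classified correctly at the bedside.

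**Working it through.** **Inputs.** From A3.h: 46 patients, 50% prevalence (23 with and 23 without dysphagia), correlation 0.3, SIS c = 0.600, increase 0.240, alpha 0.05. Assumed: two-sided alpha, an equal-variance binormal model, 0.3 taken as the latent correlation, and the SIS operating point. The plan gives no operating point for the hospital's screen, so a range is used, each pair averaging to 0.600: sensitivity/specificity of 0.60/0.60, 0.80/0.40 and 0.90/0.30.

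**1. The plan's own figure.** Hanley–McNeil variance with m = n = 23: Var(A) = [A(1−A) + (m−1)(A/(2−A) − A²) + (n−1)(2A²/(1+A) − A²)]/(mn).

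- SE at 0.600 = 0.0840; SE at 0.840 = 0.0598.
- SE of the difference = √(0.0840² + 0.0598² − 2 × 0.3 × 0.0840 × 0.0598) = 0.0872.
- Power = Φ(0.240/0.0872 − 1.96) = Φ(0.79) = 78.5%; the detectable increase at 80% power is 0.244.

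The stated 80% and 0.240 are reproduced closely.

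**2. Same operating point, different coding.** Pass/fail: c = (se + sp)/2. Graded, through the same point: c = Φ[(z(se) + z(sp))/√2]. For 0.60/0.60 this is Φ[(0.253 + 0.253)/1.414] = Φ(0.358) = 0.640. The last two columns are the simulated share of trials with 23 + 23 patients in which DeLong favours HRCA (z > 1.96; nominal 2.5%).

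| SIS se/sp | c pass/fail | c graded | gap | HRCA graded | both pass/fail |
|---|---|---|---|---|---|
| 0.60/0.60 | 0.600 | 0.640 | 0.040 | about 7% | about 3% |
| 0.80/0.40 | 0.600 | 0.661 | 0.061 | about 11% | about 3% |
| 0.90/0.30 | 0.600 | 0.704 | 0.104 | about 25% | about 3% |

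A3.b says that published screens have good sensitivity and poor specificity, which is the direction of the lower rows. For one screen in Table 3 (92%/66%), which lies outside the planned c of 0.600, the areas are 0.790 and 0.901 and the rate is about 41%.

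**3. The planned effect, like for like.** A graded HRCA with c = 0.840 has separation √2 × z(0.84) = 1.406. Cut at its midpoint, its sensitivity and specificity are both Φ(1.406/2) = 0.759. Against SIS at 0.60/0.60 the gain is 0.759 − 0.600 = 0.159 instead of 0.240. Simulated DeLong power falls from about 82% to about 45%.

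**4. Paired exact McNemar tests, 23 patients per group.**

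- SIS correct in 0.60 and HRCA in 0.759: discordant probabilities of 0.266 and 0.107, power about 14% for each of sensitivity and specificity.
- HRCA correct in 0.90, the A3.a target: discordant probabilities of 0.339 and 0.039, power about 58% for each.

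**The case against.** Three objections have weight.

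First, the documents do not say that HRCA enters as a graded score. A3.a speaks of an HRCA criterion, Aim 2 of HRCA cutoffs, and Aim 1 judges its algorithm by a confusion matrix. A3.e counts three models involving HRCA, which matches the three HRCA rules of A3.a. If both tests are pass/fail, the gap disappears. This stands: the supportable defect is unstated coding, not a demonstrated mismatch.

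Second, a reader might infer that the type I error of the planned test is 7 to 25%. That does not follow. DeLong's null is equal areas, and in those scenarios the areas truly differ. With a graded HRCA whose true area is 0.600 against a pass/fail SIS at 0.600, the simulated rate is about 3%. The aim is also superiority to SIS as delivered, so information that SIS discards by being pass/fail may fairly count against it. This stands too. What remains is that a screen must act at a cutoff, and the area difference does not show what happens there.

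Third, like-for-like comparisons have much less power with 46 patients. That is correct. It is a reason to add them and report their precision, not to replace the DeLong analysis.

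**Conclusion.** The point holds as one about specification and interpretation. A3.e and A3.a are not reconciled, and how far a c-statistic difference can be read as better detection depends on coding that is not stated. At the planned SIS c of 0.600, the built-in gap is 0.04 to 0.10 if HRCA is graded and zero if both tests are pass/fail. The sizes rest on the equal-variance binormal model and the assumed SIS operating points; the direction needs only a concave HRCA curve through the SIS point.

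A reader might conclude that a significant Aim 3 result would be an artefact. The figures do not support that: even the largest gap at c = 0.600 is less than half of 0.240, so it would inflate the planned gain and not create it. Optimism from fitting several HRCA features in 46 patients is a separate matter and is not included here.

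**What to change.** 1. State in A3.e how SIS and HRCA are coded, including how per-swallow HRCA outputs become one patient-level value, and reconcile A3.e with the four rules in A3.a.
2. Keep the DeLong comparison.
3. For each of the three HRCA-based rules in A3.a, at an HRCA cutoff locked from Aims 1 and 2 before Aim 3 data are analysed, report sensitivity and specificity with confidence intervals and paired exact McNemar comparisons with SIS. The rule requiring both tests to be positive cannot raise sensitivity above that of SIS, and the rule accepting either cannot raise specificity, so those comparisons run in one direction only. Three rules by two measures give six tests; the SAP should say which carries the claim.
4. Do not claim better detection than SIS from the c-statistic difference alone.
5. A graded SIS score built from the signs recorded in STEP 3 ("denoting any signs of OPD or penetration/aspiration (e.g., wet voice, coughs) for each swallow that is observed") can serve as a sensitivity analysis only. It is not the hospital's screen, it is unvalidated, and silent aspiration produces no such signs.

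No new data are needed. The cost is precision: the SAP should disclose the lower power shown above (about 45% by DeLong with both tests pass/fail; about 14% to 58% for each McNemar test) and treat these comparisons mainly as estimates, or revisit the sample size if they are to carry the claim.

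### Aim 3 does not say which comparison, or how many of three, must succeed: A3.h powers one unnamed HRCA strategy at 0.05, A3.e expects all three to win, and no primary comparison, order or adjustment is given

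*Combined protocol and SAP*

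**What the plan says.** All references are to the combined protocol and SAP.

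- **A3.h** (sample size): with 46 evaluable patients, half of them with the outcome, a c-statistic of 0.600 for SIS and "a correlation of approximately 0.3 between SIS and HRCA", "we will have 80% power to detect an increase in area under ROC curve as small as 0.240" at alpha 0.05, "with one of the 3 strategies that involve HRCA". The strategy is not named and sidedness is not stated.
- **A3.e** (analysis): logistic models with "HRCA signatures and SIS, both individually and in combination, as the independent variables", compared by DeLong's method. "We anticipate that the c-statistics for the 3 models involving HRCA will be significantly greater than that using SIS alone".
- **A3.a** (introduction): the working hypothesis is that "the Aspirometer combined with, and independent of, SIS will identify VF-confirmed clinically significant OPD more accurately than SIS alone". The plan is to "compare four levels of screening predictions (SIS human judgment criterion only, HRCA criterion only, SIS and HRCA criteria, SIS or HRCA criteria". A3.a also expects 90% sensitivity and 90% specificity from any one of the three HRCA strategies.
- **Specific Aims, Aim 3**: the hypothesis is a single contrast, HRCA against SIS alone. The list of predictions that follows (SIS, HRCA, SIS + HRCA) has only two that involve HRCA.
- **Table 1 and the closing text of Innovation**: the trial compares SIS with SIS + HRCA.
- **A3.f**: the benchmark for success is completed testing that yields accurate identifications. It contains no test or threshold.

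**The concern.** A3.a sets out to establish superiority over SIS and says that further development is not warranted otherwise. That is a go/no-go claim, and it needs a rule fixed in advance. Two questions are open.

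1. **Which contrast carries the claim, and how many must succeed?** A3.h reads as one of three, A3.e as all three, the Specific Aims as HRCA alone, and Table 1 as SIS + HRCA. These rules have different error rates and different power.
2. **How do the AND and OR rules of A3.a enter the models of A3.e?** Taken as main effects, A3.e's wording gives two models with HRCA (HRCA; SIS + HRCA), yet it counts three.

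While both stay open, a favourable strategy can be selected after the data are seen, and the false-claim rate cannot be calculated.

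**Working it through.** **Step 1: reproduce A3.h.** Inputs from A3.h: 23 patients with and 23 without the outcome, c = 0.600 against 0.840, r = 0.3. I take r as the correlation between the two AUC estimates and the test as two-sided; A3.h states neither.

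Hanley-McNeil variance with n = 23 per class: V(A) = [A(1−A) + (n−1)(a−A²) + (n−1)(b−A²)]/n², where a = A/(2−A) and b = 2A²/(1+A).

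- A = 0.600: a = 0.4286, b = 0.4500, V = 0.00705, SE = 0.0840.
- A = 0.840: a = 0.7241, b = 0.7670, V = 0.00358, SE = 0.0598.
- SE of the difference = √(0.00705 + 0.00358 − 2×0.3×0.0840×0.0598) = 0.0872.
- Power = Φ(0.240/0.0872 − 1.960) = Φ(0.791) = 78.5%.

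Binormal variances give 79.2 to 80.2%, and the Obuchowski approximation gives 76.9%. A standard error that also uses the null variance gives about 70% two-sided (about 81% one-sided). So 80% is about right for **one** comparison at an unadjusted two-sided 0.05.

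**Step 2: false claims if any one of three counts.** This is a simulation of 23 + 23 patients, with SIS and HRCA as pass/fail tests, DeLong variance, and within-class correlation between the tests of 0 to 0.3. Both tests are assumed to have 60% sensitivity and 60% specificity. At correlation 0:

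- AND: sensitivity 0.6×0.6 = 0.36, specificity 1 − 0.4×0.4 = 0.84, c = (0.36+0.84)/2 = 0.60.
- OR: sensitivity 0.84, specificity 0.36, c = 0.60.

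No strategy is better than SIS, so every significant result is false.

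| Rule for success | False claims |
|---|---|
| Any of three at 0.05 each, two-sided | about 12% |
| Same, counting only HRCA's favour (nominal 2.5%) | about 6% |
| Any of three at 0.05/3 each, two-sided | about 5% |
| All three, in HRCA's favour | 0.2 to 0.3% |

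Three independent tests would give 1 − 0.95³ = 14.3%. The AND/OR tests are correlated, so that figure does not apply here.

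**Step 3: power if all three must win.** Same simulation, with HRCA assumed at 84% sensitivity and specificity (c = 0.84) and SIS at 60%/60% (c = 0.60). At correlation 0:

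- AND: (0.504 + 0.936)/2 = 0.72.
- OR: (0.936 + 0.504)/2 = 0.72.

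Each gains 0.12 over SIS. Power is 75 to 89% for HRCA alone, 55 to 66% for each of AND and OR, and about 33 to 46% for all three together.

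**Step 4: adjusted power for any-of-three.** At 0.05/3 the critical value is 2.394. Hanley-McNeil power for +0.240 is Φ(2.751 − 2.394) = 63.9%; binormal variances give about 65 to 66%. The increase detectable with 80% power is about 0.27 to 0.28.

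**Step 5: does the HRCA predictor need to be fixed?** A3.e enters HRCA signatures, number unstated. With two main-effect logistic models (HRCA; SIS + HRCA) and an HRCA input that is pure noise, the chance that at least one falsely beats SIS is about 1.3 to 1.4% for a single score. With features fitted and assessed on the same 46 patients it is about 11 to 12% for three, 24 to 28% for five and 60 to 61% for eight. A testing order protects the claim only if the score is not refitted on Aim 3 data.

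**The case against.** The strongest reply is that the plan never says any one of three suffices. A3.e expects all three models to win and the A3.a hypothesis covers both combined and independent use. On that reading no adjustment is needed, as the 0.2 to 0.3% in the table shows. The Specific Aims also state one contrast, HRCA against SIS alone. This stands as far as it goes: 12% is conditional on a rule the plan does not adopt. But the plan adopts no other rule either. The all-three sentence is an anticipation, the Specific Aims contrast is not labelled primary, and Table 1 names a different one.

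A reader might also infer three stronger criticisms that the documents do not support.

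- *The combined strategies are undefined.* A3.a names them: SIS and HRCA, SIS or HRCA. What is missing is how they enter A3.e.
- *The power statement is wrong, or fails for some strategies.* It reproduces for one comparison, and A3.h claims power for one strategy, not for each. That AND and OR gain less than 0.240 in Step 3 does not contradict it.
- *The 90%/90% figure is a success threshold that settles the matter.* A3.a words it as an expectation, again for any one of the three.

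**Conclusion.** The concern holds in this form: Aim 3 has no stated rule linking the three comparisons to the superiority claim, and its sections disagree on the contrast. It should be corrected before Aim 3 data are analysed.

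The size depends on the rule. Any-of-three roughly doubles the false-claim rate (about 12% against 5% two-sided; 6% against 2.5% in HRCA's favour), assuming pass/fail AND/OR rules and 60%/60% for both tests. All-three keeps error low but leaves 33 to 46% joint power, assuming HRCA at 84%/84% and SIS at 60%/60%. One named comparison keeps the stated 80%, subject to the two-sided test and the reading of r = 0.3 in Step 1. The performance values in Steps 2 and 3 are my assumptions, chosen to match A3.h's c-statistics of 0.600 and 0.840. It cannot be concluded that the trial's error rate *is* 12%; the plan leaves it undetermined.

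**What to change.** **A3.e.** Add, for example: *The primary comparison is HRCA alone against SIS alone, by DeLong's method at two-sided 0.05, using a single HRCA score or criterion locked from Aims 1 and 2 and not refitted on Aim 3 data. If it is significant, the combined strategies are tested at two-sided 0.05 in an order fixed before Aim 3 data are analysed, stopping at the first non-significant result.* State whether the combined strategies are the AND/OR rules of A3.a or logistic models, and list each model's terms. HRCA alone is only an example; it fits the Specific Aims hypothesis and A3.h's inputs. If a combined strategy is made primary, A3.h needs inputs for that contrast.

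**A3.h.** Replace "with one of the 3 strategies that involve HRCA" by *for the primary comparison*, and state that the test is two-sided.

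**Specific Aims, Table 1 and A3.a.** Align the stated contrast with A3.e.

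**Alternatives.** If any-of-three is kept, test each at 0.05/3 and restate about 64 to 66% power for +0.240, or a detectable increase of about 0.27 to 0.28. If all three must succeed, say so and state the joint power.

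**Cost.** Wording only, with no extra patients for the primary-comparison version. The downside is that a combined strategy can be claimed only after the primary succeeds: under the Step 3 assumptions, the chance of passing HRCA alone and then an AND or OR rule is 52 to 65%. Locking the score also gives up any gain from refitting it in Aim 3.
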